11.4 Acute GVHD

The cumulative incidence of overall grades II-IV and grades III-IV acute GVHD will be assessed through six months after last dose of FMT or placebo. Grading is as detailed in Appendix F.

12. DATA REPORTING / REGULATORY REQUIREMENTS

Adverse event lists, guidelines, and instructions for AE reporting can be found in Section 7.0 (Adverse Events: List and Reporting Requirements).

12.1 Data Management

The Office of Data Quality (ODQ) will collect, manage, and perform quality checks on the data for this study.

12.2 Data Safety Monitoring

The DF/HCC Data and Safety Monitoring Board (DSMB) will review and monitor study progress, toxicity, safety and other data from this study. The Board is chaired by a medical oncologist from outside of DF/HCC and its membership composed of internal and external institutional representation. Information that raises any questions about participant safety or protocol performance will be addressed by the Overall PI, statistician and study team. Should any major concerns arise, the DSMB will offer recommendations regarding whether or not to suspend the study.

The DSMB will meet twice a year to review accrual, toxicity, response and reporting information. Information to be provided to the DSMB may include: participant accrual; treatment regimen information; adverse events and serious adverse events reported by category; summary of any deaths on study; audit results; and a summary provided by the study team. Other information (e.g. scans, laboratory values) will be provided upon request.

13. STATISTICAL CONSIDERATIONS

13.1 Primary endpoint

The primary endpoint is the proportion of patients who achieve gut microbiome diversity at one month following the final post-HCT FMT, measured by a urinary 3-IS levels (≥ 35 umol/mmol crea: gut microbiome diversity achieved; < 35 : gut microbiome diversity not achieved). A total of 48 evaluable patients will be randomized between the FMT arm and the placebo arm (24 evaluable patients per arm). Patients who are able to swallow at least one capsule will be considered as evaluable. This will give 80% power to detect a 30% improvement (20% on the placebo arm vs. 50% in the FMT arm) in the proportion of patients who achieve gut microbiome diversity at one month, with one-sided type 1 error rate of 0.12. In the primary analysis, patients who are considered as evaluable but do not have one month urinary 3-IS data available due to any reason (e.g., early death) will be included in the denominator in calculating the proportion of patients who achieve gut microbiome diversity, and will be considered as failing to achieve gut microbiome diversity at one month. A secondary analysis will also be performed, which will only include those patients with one month 3-IS data available.

13.2 Secondary endpoints

Secondary endpoints include acute GVHD at 6 months, NRM at 6 and 12 months, 100 day infection rate, PFS, OS and GRFS. All time to event outcomes will use the date of first administration of FMT (or placebo) as time 0. Definitions for these endpoints are given in section 11.

13.3 Analysis plan

The proportion of patients achieving gut microbiome diversity at one month will be compared between the FMT and the placebo arm, using a Fisher's exact test at one-sided significance level 0.12. The estimated proportions will be calculated along with 90% confidence intervals for each arm. This analysis will be performed for all evaluable patients, as well as within the subset of patients with one month 3-IS data available

The cumulative incidence of acute GVHD (using early deaths as competing risks), NRM (using relapse as competing risks), and infections (using early deaths as competing risks), will be compared between the two arms using the Gray test. The cumulative incidence for each type of endpoints will be estimated along with 90% confidence intervals for each arm. PFS, OS and GRFS will be compared using the Log-rank test, and will be estimated using the Kaplan-Meier method along with 90% confidence intervals for each arm.

13.4 Accrual

Accrual rate is expected to be approximately 24 evaluable patients per year, therefore it will take approximately 2 years to complete accrual of 48 evaluable patients.

13.5 Stopping Rule to do Death

If a participant dies due to a bloodstream infection with enteric organisms occurring within 4 weeks of final FMT dosing, the participant will be unblinded in order to determine if FMT or placebo capsules were administered. If the participant received placebo capsules, the death will not be attributed to study treatment. If the patient received FMT capsules, additional testing will be performed to assist with assessment of attribution of the infectious death. If 1 additional participant experiences a grade 5 treatment-related adverse event, the study will be terminated.

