2. BACKGROUND

2.1 HCT and the Microbiome

Allogeneic hematopoietic cell transplantation (HCT) is a potentially curative treatment for a number of malignant and non-malignant hematologic conditions. Non-relapse mortality (NRM) is a major barrier to allogeneic HCT, complicating 10-40% of all transplants, depending on patient- and transplant-related factors [Jagasia 2012, Deeg 2007]. Despite substantial advances in HLA-typing, immunosuppressive therapy, infectious disease management and supportive care, the leading causes of NRM remain GVHD and opportunistic infection. Thus, novel HCT approaches that can potentially limit such complications are of utmost importance. The recipient microbial flora may impact the development of acute GVHD [Peled, Blood 2016]. Recent focus on intestinal mucosal biology and advances in molecular techniques to simplify the complex mixtures of microorganisms have provided a better understanding of how a patient's fecal microbiome may be

associated with certain complications and overall outcomes after HCT [Teshima 2016, Morgan 2014, Taur 2015]. In HCT, the gastrointestinal mucosa is damaged, leading to an impaired intestinal microbiota with significantly reduced diversity. An analysis of fecal specimens taken from 80 recipients of allogeneic HCT at the time of engraftment showed that reduced intestinal microbiome diversity was associated with significantly worse survival outcomes (OS at 3 years was 36%, 60%, and 67% for low, intermediate and high diversity groups, respectively ($p=0.019$) [Taur 2014]. A subsequent study showed in 64 patients that increased bacterial diversity at 12 days after HCT was associated with reduced GVHD-related mortality. Furthermore, increased amounts of fecal bacteria belonging to the genus *Blautia* was specifically associated with reduced GVHD lethality [Jenq 2015]. More recently, a link between disease relapse after HCT and the abundance of several bacteria in the intestinal flora was demonstrated. In this study of 160 patients prospectively enrolled in a fecal collection protocol, *Eubacterium limosum* abundance was associated with less relapse and *Enterococcus* abundance was associated with more relapse [Peled, BBMT 2016]. While these associations between microbiome diversity and clinically important outcomes after HCT do not prove causality, the building pre-clinical evidence is compelling enough to investigate if these relationships can be altered to actually influence outcomes for patients.

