5. TREATMENT PLAN

5.1 Treatment Regimen

There will be two treatment arms. Arm 1 participants will receive **two doses of FMT after HCT**. Arm 2 participants will receive placebo capsules instead of FMTs at the same time points. Participants will be randomized in a 1:1 ratio. Double-blinding will be maintained.

An individual not involved in patient assessments will receive the randomization assignment, take appropriate capsules (either FMT (Arm 1) or placebo (Arm 2)) from relevant freezer locations, and place them on dry ice for administration. Vials will be labeled “STUDY Caps” for administration so that neither physician, research nurse, nor participant will be able to identify FMT vs. placebo capsules. The **certificate of analyses** identifying capsules as FMT or placebo will then be sealed in an opaque envelope and saved for review at the time of unblinding. This will serve as a “double-check” on actual assignment.

A total of 48 evaluable patients will be randomized between the FMT arm and the placebo arm (24 evaluable patients per arm).

Arm 1 will consist of **two (2)** doses of FMT **given after HCT**, starting within 4 weeks after engraftment after HCT.

Arm 2 will mirror Arm 1, using placebo capsules instead of FMT capsules. It will consist of **two (2)** doses of placebo, starting within 4 weeks after engraftment after HCT.

In this protocol, a standard dose of oral FMT will be defined as 15 capsules administered during on a single day. Thus 2 doses of FMT will total 30 capsules. In our previous study of FMT in patients undergoing allogeneic HCT, thirty capsules contained microbial content of a median of 38.6 g of feces (range, 24-56.7).

The FMT/placebo doses can be given within 4 weeks after engraftment after HCT. These 2 doses of oral FMT/placebo will be administered as 15 capsules per day for two days (total 30 capsules); the two days must occur within a **14** -day span – they can be consecutive, but they do not need to be.

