7.1 Expected Toxicities

In prior experiences, participants undergoing Fecal Material Transplantation experienced 24 – 48 hours of mild transient adverse events. Common events include fever, cramping, diarrhea, and gas.

Rarely participants experience bacteremia after FMT. In our institutional experience with over 400 FMT recipients (various clinical indications), there was a single incident where 2 subjects developed bacteremia from a relatively resistant organism (ESBL *E. coli*) that was later identified in the stool specimen from the same healthy FMT donor. This donor provided samples before specific screening for ESBL organisms was implemented. Additional screening will minimize this risk, but we don't believe it can be entirely eliminated.

Based on our previous experience with these subjects, special attention will be given to patients who develop bacteremia with enteric organisms within 4 weeks of FMT dosing and additional testing may be performed to assist with assessment of attribution.

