8.1.3 Storage and Stability

We do not expect, and have not previously observed a decrement in the viability or efficacy of the capsules, which will be stored at -80°C in an alarmed freezer. Capsules will be discarded if not used by their expiration date which is **9** months after encapsulation. Capsules which are not structurally intact cannot be used (see Certificate of Analysis). Representative FMT Capsules are saved for analysis in the event of infection transmission. FMT Capsule lots where numbers allow have assessment of aerobic colony forming units over time (0 and **9**months) as a measure of stability.

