11.3 Infection

Infections (bacteremia, *C. difficile*, and others) will be diagnosed per clinical norms, and testing will be at the discretion of treating physicians. Data will be collected from medical records continuously, to assess possible concurrent infection. Bacteremia with organisms typically arising from the GI tract and *C. difficile* infection are diagnoses of special interest. There will be no specific microbiological screening tests ordered for the purpose of this study.

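### Section 13.5 unblinds only deaths from one kind of infection, but its mandatory stop counts any further treatment-related death, so it can stop on a placebo death or miss two FMT-related deaths

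*Combined protocol and SAP*

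**What the plan says.** Section 13.5 begins with one class of death: "If a participant dies due to a bloodstream infection with enteric organisms occurring within 4 weeks of final FMT dosing". The 4 weeks attach to the infection, as they do in Section 7.1, where "special attention will be given to patients who develop bacteremia with enteric organisms within 4 weeks of FMT dosing". For that class the participant is unblinded, and two consequences follow. On placebo, "If the participant received placebo capsules, the death will not be attributed to study treatment". On FMT, extra testing is done to help decide attribution.

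The closing sentence sets the stop: "If 1 additional participant experiences a grade 5 treatment-related adverse event, the study will be terminated". It limits neither the cause of death nor the time since dosing.

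Elsewhere the arm is concealed. Section 5.1 says that "neither physician, research nurse, nor participant will be able to identify FMT vs. placebo capsules". It also provides for a person outside patient assessment who receives the assignment, and for a sealed certificate opened at unblinding. Section 7.2 gives a five-level attribution scale, but Section 13.5 does not say which levels make an event treatment-related. Section 12.2 lets the DSMB recommend suspension. Section 13.5 is the only mandatory stopping rule.

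**The concern.** The deaths that the rule unblinds are a narrower set than the deaths it counts. The placebo exemption depends on the unblinding, so it does not reach deaths from other causes. The rule can therefore err in two directions.

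- **Wrong stop.** After a first death in the named class on FMT, a second death outside the class is attributed by people who do not know the arm. If it is judged related and the participant had received placebo, the study terminates on a death that FMT cannot have caused.
- **Missed stop.** The only first event that the rule describes is in the named class. Two FMT-related deaths from other causes never start the count.

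Attribution will be difficult in this population. Section 2.1 describes non-relapse mortality as "complicating 10-40% of all transplants", so deaths that call for a judgement are likely in both arms. A mandatory stop has to be applicable when a death occurs, without argument over which deaths count.

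**Working it through.** Section 13.5 states no operating characteristic, so there is no figure of the plan's own to reproduce. The check is first textual; the arithmetic that follows is illustrative.

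**Step 1. Is there another route to unblinding or counting?** Section 5.1 describes how the assignment is held, but gives no trigger for opening it after a death. Section 7.1 concerns enteric bacteremia only. Section 7.2 defines attribution, Sections 7.3 and 7.4 cover reporting, and Section 12.2 covers DSMB advice. None unblinds a death outside the named class or adds it to a count.

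**Step 2. Does a different reading of *additional* repair the rule?**

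| Reading | Stop on a blind-attributed placebo death? | Two FMT-related deaths outside the class missed? |
|---|---|---|
| Literal: first death in the class, second of any cause | Possible | Yes |
| Second death must also be in the class | No | Yes; no outside-class death ever counts |
| Any two treatment-related deaths | Possible | No |

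Every reading leaves at least one fault.

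**Step 3. Missed stop, literal reading.** Let f be the share of FMT-related deaths outside the class. The documents give no value, so 25%, 50% and 75% are assumed. Given exactly two FMT-related deaths:

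- both outside the class: f² = 6%, 25%, 56%;
- outside-class death first, in-class death second: f(1 − f) = 19%, 25%, 19%. The text does not say whether the count is then two.

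Without that condition the figures are small. Take 24 FMT patients (Section 13.1) and an assumed 2% risk of FMT-related death. The chance of two or more such deaths is 1 − 0.98^24 − 24 × 0.02 × 0.98^23 = 8.3%. The chance of two or more with none in the class is (1 − 0.02(1 − f))^24 − 0.98^24 − 24 × 0.02f × 0.98^23 = 0.5%, 1.9% and 4.5% for the three values of f. At 1% risk and f = 50% it is about 0.6%.

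**Step 4. Wrong stop, literal reading.** After one in-class FMT death, 24 placebo and 23 FMT patients remain. Let r be the ratio, FMT to placebo, of outside-class deaths judged related while blind (assumed). The placebo share of the stops that such deaths cause is 24 / (24 + 23r):

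- r = 1: 24/47 = 51%;
- r = 2: 24/70 = 34%;
- r = 3: 24/93 = 26%.

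These are shares of stops given that first death, not probabilities of a wrong stop.

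**Step 5. How a corrected rule would behave.** If each of 24 FMT patients has probability p (assumed) of a death that counts, the chance of reaching two is 1 − (1 − p)^24 − 24p(1 − p)^23:

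| p | 0.5% | 1% | 2% | 5% | 10% |
|---|---|---|---|---|---|
| Chance of stopping | 0.6% | 2.4% | 8.3% | 34% | 71% |

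**Step 6. Background deaths.** At 10% to 40% non-relapse mortality, 48 patients give 4.8 to 19.2 deaths, of which 2.4 to 9.6 would be on placebo. That range is for all transplants and is probably high for patients dosed after engraftment.

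**The case against.** The strongest reply is that this is loose drafting around one known hazard. Section 7.1 reports two FMT recipients who developed resistant *E. coli* bacteremia from the same donor, and Section 13.5 targets exactly that. If *additional* means a second death of the same kind, both deaths are unblinded and the wrong stop disappears. Other deaths are still watched: serious events go to the overall PI (7.3.1), all grade 5 events to the IRB office (7.3.2), and unexpected fatal events associated with treatment to FDA within 7 calendar days (7.4). The DSMB reviews deaths and can recommend suspension (12.2).

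Much of this stands. The history explains the special testing, and two FMT-related deaths would not go unreviewed. But the stop is worded for any treatment-related death, and the narrow reading leaves every other FMT-related death uncounted. Reporting and advice do not supply the missing count or unblinding step.

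Three stronger inferences are tempting but unsupported.

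- *The plan itself foresees fatal FMT harm outside the class.* A reader might cite Section 11.3, where gut-origin bacteremia and *C. difficile* "infection are diagnoses of special interest", or Section 8.1.3: "Representative FMT Capsules are saved for analysis in the event of infection transmission". Section 11.3 lists outcomes to be measured, and Section 2.2 presents FMT as a treatment for *C. difficile*. Section 8.1.3 also covers the bacteremia already in the class.
- *The first death need not be related to FMT.* The word *additional* and the attribution testing both imply that it must be.
- *A placebo death in the named class could count.* Section 13.5 expressly excludes it.

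**Conclusion.** The concern holds as a fault in the stated rule. Followed literally, it can terminate the study on a placebo death attributed while blind, and it does not trigger automatically after two FMT-related deaths outside the named class. Choosing another reading exchanges one fault for the other. This conclusion rests on the text alone.

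The percentages depend on f, r and the death risks, none of which the documents give. They are conditional illustrations, and no overall probability of a wrong or missed stop is claimed. Severity is minor to moderate: this is the only mandatory safety stop, but reporting and DSMB review limit the harm. Sample size and the primary analysis do not depend on it.

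**What to change.** Reword Section 13.5 along these lines:

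> Every grade 5 event that the blinded investigator judges treatment-related, at the attribution level specified here, will be unblinded before it is counted, whatever its cause, by a person outside the assessment team. Deaths in placebo recipients do not count. The study terminates at the second such death among FMT recipients.

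Keep the present unblinding and extra testing for enteric bloodstream infection deaths. The threshold of two appears to be the existing intent. The sponsor and DSMB should confirm it and fix the attribution level in advance from the Section 7.2 scale.

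The cost is a few sentences. The person who receives the assignment under Section 5.1 already exists. A few more participants are unblinded, all of them deceased and only those whose deaths are judged related. Recording that judgement before the arm is revealed keeps knowledge of the arm from influencing it.

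The main downside is the attribution level. If a low threshold such as *possible* lets in background deaths at 5% to 10% of FMT patients, the calculation for the corrected rule shows that the study would often stop for reasons unrelated to FMT. A stricter level reduces that risk but may leave out a true FMT-related death whose cause is uncertain.

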APPENDIX A PERFORMANCE STATUS CRITERIA

ECOG Performance Status Scale		Karnofsky Performance Scale	
Grade	Descriptions	Percent	Description
0	Normal activity. Fully active, able to carry on all pre-disease performance without restriction.	100	Normal, no complaints, no evidence of disease.
		90	Able to carry on normal activity; minor signs or symptoms of disease.
1	Symptoms, but ambulatory. Restricted in physically strenuous activity, but ambulatory and able to carry out work of a light or sedentary nature (e.g., light housework, office work).	80	Normal activity with effort; some signs or symptoms of disease.
		70	Cares for self, unable to carry on normal activity or to do active work.
2	In bed <50% of the time. Ambulatory and capable of all self-care, but unable to carry out any work activities. Up and about more than 50% of waking hours.	60	Requires occasional assistance, but is able to care for most of his/her needs.
		50	Requires considerable assistance and frequent medical care.
3	In bed >50% of the time. Capable of only limited self-care, confined to bed or chair more than 50% of waking hours.	40	Disabled, requires special care and assistance.
		30	Severely disabled, hospitalization indicated. Death not imminent.
4	100% bedridden. Completely disabled. Cannot carry on any self-care. Totally confined to bed or chair.	20	Very sick, hospitalization indicated. Death not imminent.
		10	Moribund, fatal processes progressing rapidly.
5	Dead.	0	Dead.

APPENDIX B FMT INVESTIGATOR’S BROCHURE
 Investigators Brochure
 MGH FMT Frozen Capsules

[name] Laboratory
 [name]
 Infectious Disease Division

Department of Medicine
 Massachusetts General Hospital

Principal Investigator: [name] MD

Version: 9.0
 Date: June 4, 2019

The purpose of this document is to provide co-investigators with concise, current information about FMT capsules, direction for dosing, and active state of knowledge about their use. Information included is current as of June 4, 2019 and includes subjects receiving one or more doses of FMT capsules.

This document will be updated at least annually.

Capsule Overview

FMT capsules are made from stool donated by healthy individuals 18-50 who must pass a careful health screening, including blood banking questionnaire, medical history, physical exam, and numerous blood and fecal tests as shown below. Fecal material is blenderized in sterile preservative-free saline, and then sieved, pelleted, and re-suspended in sterile saline/40% glycerol and double encapsulated in pharmaceutical grade, nested vegan hypromellose capsules designed to open in neutral pH environments (Capsugel). Capsules are then frozen. One standard dose of thirty capsules contains soluble material harvested from approximately 40 grams of fecal material. Manufacturing details are in separate Clinical Manufacturing and Control documents.

Done at screening within 30 days of start of donations	General Health Laboratory Tests
	C-Reactive protein, high sensitivity
	Lipid panel
	Comprehensive metabolic panel
	CBC with differential
	ANA – sent out to Mayo
	HTLV I & II antibodies
	Pregnancy test by HCG if female
Done at screening within 30 days of start of donations *re-done with stool samples from first and last donations	Stool Tests
	Clostridium difficile testing by PCR
	Stool culture for enteric pathogens* – includes Yersinia , Vibrio cholerae , V. parahemolyticus , and E. coli O157
	Rotavirus antigen detection by ELISA
	Ova and parasites – includes giardia and cryptosporidium
	Norovirus
	Adenovirus
	VRE rectal screen
	MRSA nasal screen
	Helicobacter pylori – sent out to Mayo

	MRSA plating*
	Listeria plating*
	CRE plating*
	ESBL plating*
Done at screening within 30 days of start of donations	Serologic Tests
	Hepatitis A (IgG + IgM)
	Hepatitis B (surface Ag + surface Ab)
	Hepatitis C (IgG)
Repeated 28-40 days after last donation	HIV 1/2 (IgG)
	Syphilis TrepSure ELISA
Done at the time of the first and last donations	Viral Loads
	Epstein-Barr virus
	Cytomegalovirus
Optional – done at screening	Oral Glucose Tolerance Test – Optional
	Glucose (fasting)
	Hemoglobin A1C
	Glucose tolerance test, 2 hours post glucola ingestion

Appearance

Exemplary capsules are shown below.

Storage

Capsules are frozen and stored at -80°C and shipped on dry ice. A dated certificate of analysis which includes lot number, and manufacture date, acceptance of donor testing, and structural integrity of capsules at the time of shipment or in person delivery on dry ice to an investigator for a specific recipient will be filed. It is recommended that capsule be stored no longer than 30 days at -20°C, in a FROST-FREE freezer. Capsules should be discarded 9 months after manufacture. Capsules should be promptly transported on dry ice once removed from the freezer, for administration to subjects.

Animal testing

No animal testing has been performed on FMT capsules.

Solubility

FMT capsules and prototypes with aqueous dyes are demonstrated to be relatively stable in an acid environment and release payload under neutral conditions. It is

therefore NOT required nor recommended that subjects take antacids, bicarbonate or other acid-suppressing medications prior to administration. Taking these medications are not contraindications to administration of FMT capsules however.

Instructions for Use

Subjects must meet study-specified inclusion and exclusion criteria. Subjects should be NPO for 4 hours prior to and one hour after administration of capsules.

For treatment of *C. difficile* infection (CDI)

A single dose is considered 30 capsules when treating CDI. Capsules may be administered on 2 successive days (15 each day) or 3 successive days (10 each day), at the choice of subject/physician. For simple convenience most people prefer 2 days. Subjects or parents should sign a clinical consent form. Follow-up phone calls and completion of the 2-sided follow-up Case Report Form provided are required at the following intervals

- in the 24-96 hours window after administration
- at 7-14 days
- at 8 weeks (+/- 5 days)
- at 6 mo (+/- 2 weeks)

and subjects should be seen in person as dictated by a physician's clinical judgment. Physicians who do not complete and return follow-up forms in a timely manner will not be provided additional capsules.

For other applications, doses will be defined within specific clinical protocols, but will generally follow the above timing for safety assessments.

Acute reactions after dosing in 403 subjects treated for *C. difficile*

The capsules are tasteless and odorless. Five adult subjects and two children of 403 total have vomited within 8-12 h after capsule administration and **not** brought up feculent material or intact capsules. One cancer patient with chronic vomiting of medications vomited up all 15 capsules of his second dose, after tolerating the first dose well. Diarrhea and irritable bowel-like symptoms are commonly reported after FMT for CDI and often resolve over time. Subjects may be discharged after explanation of follow-up and advised re diet, relapse and AE's to monitor which usually takes about 20 minutes.

Total Adverse Events in 395 subjects reaching 8 weeks follow-up

Most subjects treated for CDI have some ongoing GI symptoms, typically minor (Grade 1). It is impossible to determine if these symptoms are related to resolving CDI, post-infectious irritable bowel syndrome, or the capsules themselves. See Chart 1 below. One IBD flare requiring intensified treatment has been noted and deemed related.

EVENT	Number	Percentage
Fevers - transient	9	3%
Hospitalizations	44	16%
Deaths	24	8%

Diarrhea	145	48%
Nausea/bloating	78	25%
Ulcerative colitis flare	3	0.01%

Expected resolution of symptoms of *C. difficile*.

This is variable. The occasional individual has fever, cramping, borborygmi and occasional diarrheal bowel movements after dosing. Patients with significant abdominal pain as part of their presenting or ongoing symptoms may have a component of Irritable Bowel Syndrome. Episodic pain or nonspecific abdominal discomfort may persist. Some subjects resolve diarrhea but have ongoing frequent formed stools compared with baseline. In the MGH experience, some subjects have cleared stool of *C. difficile* based upon repeated testing, but had slow resolution of other symptoms over weeks. Cure is defined as resolution of diarrhea at 8 weeks (3 stools or less per day).

Definition of Relapsed CDI

A relapse qualifying for re-dosing must meet the following criteria:

- Relapsed or ongoing diarrhea (more than 4 bowel movements of Bristol Grade 3 or higher AND
- A positive stool test for *C. diff* (toxin or PCR) on day 5 or later (Day 0 = initial dose day). Routine rescreening of stools in the absence of significant symptoms is not recommended.

